11.4 Calculation or derivation of pharmacokinetic variables

PK analysis of the plasma concentration data for olaparib will be performed at AstraZeneca R&D or by a CRO identified by AstraZeneca R&D. The actual sampling times will be used in the PK calculations. For each patient providing a complete set of PK samples, non-linear mixed effects modelling (NONMEM) will be used to estimate steady state Cmax, AUC and Cmin.

11.5 Calculation or derivation of pharmacodynamic variable(s) not applicable

11.6 Calculation or derivation of pharmacogenetic variables

To be defined in an exploratory analysis plan.

11.7 Calculation or derivation of health economic variables

Frequency of resource use including type, length of stay and procedures undertaken, and the primary symptom/reason for the hospitalisation or hospital attendance will be estimated.

12. STATISTICAL METHODS AND SAMPLE SIZE DETERMINATION BY ASTRAZENECA

[figure not shown]
12.1 Description of analysis sets

A comprehensive statistical analysis plan (SAP) will be prepared and finalised before first patient in.

Table 9 gives a summary of outcome variables and analysis populations.

12.1.1 Full analysis set

Intention to treat (ITT): The primary statistical analysis of the efficacy of olaparib will include all randomised patients and will compare the treatment groups on the basis of randomised treatment, regardless of the treatment actually received. Patients who were randomised but did not subsequently go on to receive study treatment are included in the Full Analysis Set (FAS). Therefore, all efficacy and health-related QoL data will be summarised and analysed using the FAS on an intention-to-treat (ITT) basis.

12.1.2 Safety analysis set

All patients who received at least one dose of randomised study treatment, olaparib or chemotherapy, will be included in the safety analysis set. If a patient receives at least one dose of olaparib they will be summarised in the olaparib arm for safety summaries (e.g. olaparib arm will include patients randomised to olaparib who receive at least one dose of olaparib or chemotherapy patients who receive at least one dose of olaparib in error at any time). If a patient randomised to olaparib receives only chemotherapy treatment then they will be summarised as part of the chemotherapy arm.

12.1.3 Evaluable for response (EFR) analysis set

This is a subset of the ITT population, who have measurable disease at baseline as per the RECIST 1.1 criteria. Measurable disease will be defined using the BICR data for analyses of BICR data and using the investigator assessment data for analyses of investigator assessment.

12.1.4 PK Analysis set

PK data will be analysed according to treatment received. This population will comprise all patients who receive study treatment as per protocol (PP) and do not violate or deviate from the protocol in ways that would significantly affect the PK analyses. The population will be defined by the Study Team Physician, Pharmacokineticist and Statistician prior to any analyses being performed.

Table 9 Summary of Outcome Variables and Analysis Populations

Outcome Variable	Populations
Efficacy Data	
- PFS	FAS (ITT)
- OS, PFS2, objective response rate, symptom/QoL endpoints	FAS (ITT)
Demography	FAS (ITT)
Pharmacokinetic data	PK
Safety Data	
- Exposure	Safety
- Adverse Events	Safety
- Lab measurements	Safety
- Vital Signs	Safety

12.2 Methods of statistical analyses

The treatment comparison is olaparib 300 mg bid vs physician's choice of chemotherapy.

Results of all statistical analysis will be presented using a 95% confidence interval and 2-sided p-value.

The following table details which endpoints are to be subject to formal statistical analysis, together with pre-planned sensitivity analyses making clear which analysis is regarded as primary for that endpoint

Table 10 Formal Statistical Analyses to be Conducted and Pre-Planned Sensitivity Analyses

Endpoints Analysed	Notes
PFS (Time from randomisation to first progression or death)	Primary analysis stratified log-rank test using BICR data
	Sensitivity/supportive analyses ^a :
	1) Evaluation time bias analysis; stratified log-rank test using BICR data
	2) Attrition bias analysis (using alternative censoring rules); stratified log-rank test using BICR data
	3) Ascertainment bias analysis; stratified log-rank test using Investigator data
	4) Deviation bias (if meaningful to do); stratified log-rank test using BICR data
	5) Stratified log rank test of time from randomisation to first subsequent therapy or death 6) stratified log rank test using BICR data in randomised patients confirmed as BRCA mutation positive by central Myraid test (if applicable)
Overall Survival (Time from randomisation to death due to any cause)	Primary analysis: stratified log-rank test Supportive analysis: KM plot of time to censoring for OS
PFS2 (Time from randomisation to second progression or death)	Primary analysis: Stratified log rank test based on investigator assessment of second progression Supportive analysis: Stratified log rank test of time from randomisation to second subsequent therapy or death
Objective Response Rate (Number of patients who have a CR or PR determined using RECIST 1.1 criteria divided by the number of patients with measurable disease.)	Primary: ORR per treatment arm (descriptive only) based on BICR data Supportive: ORR per treatment arm (descriptive only) based on investigator assessment

Table 10 Formal Statistical Analyses to be Conducted and Pre-Planned Sensitivity Analyses

Endpoints Analysed	Notes
Adjusted mean change from baseline in global QoL score from the EORTC QLQ-C30 questionnaire	Primary analysis: mixed model for repeated measures (MMRM) analysis of all of the post-baseline scores for each visit

^a See Section 12.2.2.1 for further details

12.2.1 Multiplicity strategy for primary and key secondary endpoints

In order to describe the nature of the effects of olaparib compared to chemotherapy, PFS, PFS2, and OS will be tested at a two-sided significance level of 5%.

In addition to these planned analyses, which will be performed and reported in the CSR, in order to strongly control the type I error at 2.5% (one-sided) for key label claims, a multiple testing procedure (MTP) will be employed across the primary endpoint (PFS) and key secondary endpoints (PFS2 and OS).

A hierarchical testing strategy will be employed where PFS will be tested first using the full test mass (full test mass = alpha 2.5% one-sided) and key secondary endpoints of PFS2 and OS will then be tested using the MTP with a recycling strategy (i.e., the MTP will recycle the test mass to the endpoint not yet rejected in the hierarchy outlined in Figure 2). The MTP is detailed below.

Figure 2 Multiple Testing Procedure

PFS2 will only be tested if statistical significance is shown for PFS. OS will only be tested if statistical significance is shown for PFS2. This testing will occur at the time of the primary PFS analysis (approximately 230 PFS events), and again when there are approximately 60% deaths (approximately 190 OS events). The Lan and DeMets approach that approximates the O'Brien & Fleming spending function will be employed to preserve the overall 1-sided type-I error rate of 2.5% (Lan and DeMets 1983).

If the first analysis for PFS2 occurs at exactly 180 PFS2 events (58% overall data maturity predicted at the time of the primary PFS analysis), statistical significance for PFS2 will be declared if the null hypothesis for PFS is rejected and the observed one-sided p-value for

PFS2 is $p < 0.007$, which equates to a HR of ≤ 0.68 . The significance level at the final analysis will be determined based on the exact number of events at the time of the first and final analyses. If the first analysis for PFS2 occurs at exactly 180 PFS2 events and the final analysis occurs at exactly 255 PFS2 events, then the significance level to be applied at the final analysis will be 2.3%. Statistical significance for PFS2 will be declared if the observed p-value for PFS2 is $p < 0.023$, which equates to a HR of ≤ 0.77 .

If the first analysis for OS occurs at exactly 114 OS events (37% overall data maturity predicted at the time of the primary PFS analysis), statistical significance for OS will be declared if the null hypotheses for PFS and PFS2 are rejected and the observed one-sided p-value for OS is $p < 0.004$, which equates to a HR of ≤ 0.59 . If the first analysis for OS occurs at exactly 114 OS events and the final analysis occurs at exactly 190 OS events, then the significance level to be applied at the final analysis will be 2.4%. Statistical significance for OS will be declared if the observed p-value for OS is $p < 0.024$, which equates to a HR of ≤ 0.74 .

12.2.2 Analysis of primary endpoint

PFS will be analysed when approximately 230 progression events have occurred, based on the BICR data. No further analyses of PFS are planned beyond this point unless requested by Health Authorities.

PFS will be analysed using a log rank test stratified by the stratification factors. The hazard ratio (HR) and confidence interval will be estimated from the U and V statistics obtained directly from the LIFETEST model with inclusion of STRATA terms for the stratification variables (and using the Breslow approach for handling ties).

The HR and its confidence interval will be estimated from the log-rank as follows ([Berry et al 1999](#) and [Sellke et al 1983](#))

$$\text{HR} = \exp(U/V)$$

$$95\% \text{ CI for HR} = (\exp\{U/V - 1.96/\sqrt{V}\}, \exp\{U/V + 1.96/\sqrt{V}\})$$

Where $U = \sum_i (d_{1i} - e_{1i})$ is the log-rank test statistic (with d_{1i} and e_{1i} the observed and expected events in group 1) and \sqrt{V} the standard deviation of the log-rank test statistic as produced in the LIFETEST output.

The HR (olaparib vs chemotherapy) together with its corresponding 95% confidence interval (CI) and p-value will be presented (a HR less than 1 will favour olaparib).

Stratification variables will be defined according to data from the interactive voice/web response system (IVRS/IWRS). If there are any patients who were mis-stratified, a sensitivity analysis will be carried out using the (correct) baseline data collected in the eCRF.

A Kaplan-Meier (KM) plot of PFS will be presented by treatment group. Summaries of the number and percentage of patients experiencing a PFS event, and the type of event (RECIST or death) will be provided along with median PFS for each treatment arm.

The assumption of proportionality will be assessed. Note that in the presence of non-proportionality, the HR will be interpreted as an average HR over the observed extent of follow-up. Proportionality will be tested firstly by producing plots of complementary log-log (event times) versus log (time) and, if these raise concerns, a time dependent covariate would be fitted to assess the extent to which this represents random variation.

The primary analysis will be based on the programmatically derived PFS based on BICR assessments, and using all scans regardless of whether they were scheduled or not.

The estimated PFS rates at 6 months and 12 months will be summarised (using the KM curve) and presented by treatment group.

The number of patients prematurely censored will be summarised by treatment arm together with baseline prognostic factors of the prematurely censored patients. A patient is defined as prematurely censored if they had not progressed and the latest scan prior to DCO was more than one scheduled tumour assessment interval (+ 2 weeks) prior to the DCO date.

As patients will be randomised, imbalances in demographic factors between the treatment groups are not anticipated. However if any imbalances should occur, the HR and associated confidence interval calculated from a Cox Proportional Hazards model containing treatment, stratification variables and these additional demographic variables, may be reported.

Subgroup analyses will be conducted comparing PFS between treatments. The purpose of the subgroup analyses is to assess the consistency of treatment effect across potential or expected prognostic factors. If there are too few events available for a meaningful analysis of a particular subgroup (it is not considered appropriate to present analyses where there are less than 20 events in a subgroup), the relationship between that subgroup and PFS will not be formally analysed. In this case, only descriptive summaries will be provided

The following subgroups of the full analysis set will be analysed for PFS

Stratification factors

- Received prior chemotherapy regimens for metastatic breast cancer (yes/no)
- ER and/or PgR positive vs ER and PgR negative
- Prior platinum for breast cancer (yes/no)

Additional subgroups of interest include:

- Progressive disease at time of randomisation (yes/no)

- Measurable versus non measurable disease
- *BRCA* mutation type, e.g. *BRCA1*, *BRCA2* or *BRCA1/2* (both)
- Age at randomisation
- Region
- Race

Other baseline variables may also be assessed if there is clinical justification.

For each subgroup, the HRs (olaparib: physician's choice of chemotherapy) and associated CIs will be calculated from a Cox proportional hazards model (ties = Efron) that contains the treatment term, factor and treatment-by-factor interaction term. The treatment effect HRs for each treatment comparison along with their confidence intervals will be obtained for each level of the subgroup from this single model. The HRs and 95% CIs will be presented on a forest plot including the HR and 95% CI from the overall population (using the primary analysis).

No adjustment to the significance level for testing of subgroups will be made since all these subgroup analyses will be considered exploratory and may only be supportive of the primary analysis of PFS.

The presence of quantitative interactions will be assessed by means of an overall global interaction test. This will be performed in the overall population by comparing the fit of a Cox proportional hazards model including treatment, all covariates (stratification factors), and all covariate-by-treatment interaction terms, with one that excludes the interaction terms and will be assessed at the 2-sided 10% significance level. If the fit of the model is not significantly improved then it will be concluded that overall the treatment effect is consistent across the subgroups.

If the global interaction test is found to be statistically significant, an attempt to determine the cause and type of interaction will be made. Stepwise backwards selection will be performed on the saturated model, whereby (using a 10% level throughout) the least significant interaction terms are removed one-by-one and any newly significant interactions re-included until a final model is reached where all included interactions are significant and all excluded interactions are non-significant. Throughout this process all main effects will be included in the model regardless of whether the corresponding interaction term is still present. This approach will identify the factors that independently alter the treatment effect and prevent identification of multiple correlated interactions.

Any quantitative interactions identified using this procedure will then be tested to rule out any qualitative interaction using the approach [Gail and Simon 1985](#).

A further analysis of PFS (using Investigator assessed RECIST) may be performed at the time of the OS analyses, if requested by Health authorities.

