3.1 Overall study design and flow chart

This open label, randomised, controlled, multi-centre phase III study will assess the efficacy and safety of single agent olaparib vs standard of care based on physician's choice of capecitabine, vinorelbine or eribulin in metastatic breast cancer patients with *gBRCA1/2* mutations. Due to different routes and schedules of administration of the treatment options

on the control arm as well as their different toxicity profiles, the study cannot be blinded. Given the open label design of the study, rigorous methodology will be employed to ensure robustness of the primary endpoint assessment with a primary analysis of PFS based on blinded independent central review (BICR) of all patient scans. Secondary endpoints will include overall survival, PFS2, ORR by BICR, safety assessments and health related quality of life.

Approximately 310 patients will be randomised 2:1 (olaparib:chemotherapy) into the trial. The treatment groups include olaparib 300 mg po bid daily tablet continuous, or physician's choice of chemotherapy from one of the following regimens. The investigator must declare prior to randomisation their choice of chemotherapy i.e. capecitabine or vinorelbine or eribulin.

- Capecitabine 2500 mg/m² po daily (divided in 2 doses) x 14 days, repeat every 21 days
- Vinorelbine 30 mg/m² IV Day 1 and Day 8, repeat every 21 days
- Eribulin mesylate 1.4 mg/m² or Eribulin (active substance) 1.23mg/m² IV Day 1 and Day 8, repeat every 21 days

The randomisation scheme will be stratified based on:

- Received prior chemotherapy regimens for metastatic breast cancer (yes/no)
- ER and/or PgR positive vs ER and PgR negative
- Prior platinum for breast cancer (yes/no)

Target patient population

All patients recruited in the study will be selected based on the following 3 principles:

- **Genetic selection:** Documented germline mutation in *BRCA1* or *BRCA2* that is predicted to be deleterious or suspected deleterious (known or predicted to be detrimental/lead to loss of function). Patients with *BRCA1* and/or *BRCA2* mutations that are considered to be non detrimental (eg. "Variants of uncertain clinical significance" or "Variant of unknown significance" or "Variant, favor polymorphism" or "benign polymorphism," etc) will not be eligible for the study.

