12.2.2.1 Sensitivity Analyses for Primary Endpoint

As a sensitivity analysis to the primary endpoint of PFS, the primary analysis will be repeated excluding any patients who did not have a *gBRCA* mutation status confirmed by the Myriad test. The same methodology and model will be used and the HR and associated 95% CI from a Cox Proportional Hazards model will be reported.

Sensitivity analyses will be performed to assess the possible presence of time-assessment bias (i.e., differential assessment times between treatment groups).

Summary statistics for the number of weeks between the time of progression and the last evaluable RECIST assessment prior to progression will be presented for each treatment group.

(a) Evaluation-Time bias

Sensitivity analyses will be performed to assess possible evaluation-time bias that may be introduced if scans are not performed at the protocol-scheduled time points. The midpoint between the time of progression and the previous evaluable RECIST assessment will be analysed using a stratified log rank test, as described for the primary analysis of PFS. This approach has been shown to be robust to even highly asymmetric assessment schedules ([Sun and Chen 2010](#)). This approach will use the BICR RECIST assessments.

(b) Attrition bias

Attrition bias will be assessed by repeating the primary PFS analysis except that the actual PFS event times, rather than the censored times, of patients who progressed or died in the absence of progression immediately following two, or more, non-evaluable tumour assessments will be included. In addition, patients who take subsequent therapy prior to progression or death will be censored at their last evaluable assessment prior to taking the subsequent therapy.

Additionally a Kaplan-Meier plot of the time to censoring where the censoring indicator of the primary PFS analysis is reversed will be presented.

(c) Ascertainment bias

A stratified log-rank test will be repeated using the programmatically derived RECIST using Investigator assessed PFS. The HR and 95% Confidence Interval will be presented.

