12.3 Determination of sample size

The sample size for this study was selected to be consistent with the research hypothesis as described in Section 1.

The primary endpoint of the study is PFS. In total 230 PFS events in the study would have 90% power to show statistically significant PFS at the one-sided 2.5% level if the assumed true treatment effect were HR 0.635; this translates to an approximate 2 month clinically relevant improvement in median PFS over an assumed 4 month median PFS on chemotherapy assuming PFS is exponentially distributed.

Approximately 310 patients will be recruited (2:1 ratio) so that data maturity for the PFS analysis is approximately 75%.

It is estimated that the study recruitment period will be approximately 22 months and that 230 progression events will have occurred approximately 27 months after the first patient is randomised in the study. This will be the primary analysis of PFS. No further analyses of PFS are planned beyond this point unless requested by Health Authorities.

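### The primary PFS hazard ratio is a one-step log-rank estimate: under 2:1 allocation and a real effect it leans moderately towards olaparib, and its 95% CI covers about 92–93%

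*Protocol*

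**What the plan says.** Section 12.2.2 tests PFS with a log-rank test stratified by the three randomisation factors. For the effect size it states: "The hazard ratio (HR) and confidence interval will be estimated from the U and V statistics obtained directly from the LIFETEST model". It writes the formula out as HR = exp(U/V), with 95% limits exp(U/V ± 1.96/sqrt(V)), where sqrt(V) is "the standard deviation of the log-rank test statistic as produced in the LIFETEST output". The ratio is olaparib to chemotherapy, so that "a HR less than 1 will favour olaparib". The same sentence names Breslow for ties.

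Sections 12.2.2.1, 12.2.3.1 and 12.2.3.2 carry the method over to time to first subsequent therapy (TFST), PFS2, time to second subsequent therapy (TSST) and OS.

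Elsewhere the protocol uses a different estimator:

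- Subgroups (Section 12.2.2): "associated CIs will be calculated from a Cox proportional hazards model (ties = Efron"). These HRs share a forest plot with the overall result, "including the HR and 95% CI from the overall population (using the primary analysis").
- Patients confirmed by the Myriad test (Section 12.2.2.1): the primary method and model are to be repeated, yet "the HR and associated 95% CI from a Cox Proportional Hazards model will be reported".
- An overall Cox HR appears only as an optional extra if demographic imbalances arise.

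The design is unequal: "Approximately 310 patients will be randomised 2:1 (olaparib:chemotherapy) into the trial".

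**The concern.** U and V come from the log-rank test, so both are computed as if HR were 1. exp(U/V) is one step from that point towards the maximum-likelihood estimate, and 1/sqrt(V) is its standard error under the null. Both are good approximations near HR 1. With equal allocation the one-step estimate stays close to the truth for moderate effects. With two thirds of patients on the better arm, and a risk set that becomes more olaparib-heavy as controls progress sooner, the step overshoots away from 1 and the null variance is too small. The reported HR would then flatter olaparib somewhat, and the interval would miss the truth more often than 5%, mostly on the favourable side. The protocol itself writes the formula in full, so this is not a detail left to the SAP.

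**Working it through.** **Inputs.** From the protocol: estimator and three binary factors, hence 8 strata (Section 12.2.2); 310 patients, 2:1, scans every 6 weeks to week 24 and every 12 weeks after, each ±1 week (Section 3.1); 230 events, HR 0.635, exponential PFS with a 4-month control median, 22-month recruitment (Section 12.3). Assumed, because the protocol does not give them: stratum prevalences and prognostic effects, uniform accrual, no dropout.

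**1. Reproduce the plan's own figures.** Section 12.3 states: "In total 230 PFS events in the study would have 90% power to show statistically significant PFS at the one-sided 2.5% level". The Schoenfeld formula gives d = (1.960 + 1.282)² / [(2/9) × (ln 0.635)²] = 10.51 / (0.2222 × 0.2062) ≈ 229.3, so 230 events; power with 230 is 0.901. A 1:1 split would need 204, so the plan did allow for 2:1. The critical HRs in Section 12.2.1 also reproduce, as exp(−z/sqrt(2d/9)): 0.678, 0.767, 0.590 and 0.738, against the stated 0.68, 0.77, 0.59 and 0.74.

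**2. Closed form.** Let p be olaparib's share of the risk set. Per event, U has mean p·HR/(p·HR + 1 − p) − p, and V = p(1 − p). Hence:

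- U/V tends to (HR − 1)/(p·HR + 1 − p);
- true variance over nominal variance = HR/(p·HR + 1 − p)².

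At HR 0.635 and p = 2/3: p·HR + 1 − p = 0.4233 + 0.3333 = 0.7567; −0.365/0.7567 = −0.482; exp(−0.482) = 0.617. Variance ratio: 0.635/0.7567² = 1.11.

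| p | exp(U/V) tends to | variance ratio |
|---|---|---|
| 0.50 | 0.640 | 0.95 |
| 0.667 | 0.617 | 1.11 |
| 0.72 | 0.610 | 1.17 |
| 0.75 | 0.605 | 1.20 |

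The bias therefore comes from combining this estimator with unequal allocation. Swapping the arms changes the sign of U and leaves V alone, so the choice of group 1 does not matter.

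**3. Simulation.** Cut-off at the 230th event, continuous event times, 3,000 to 5,000 trials per case; Monte Carlo standard error of coverage 0.3–0.4 points. Mean HR is geometric.

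| Case | exp(U/V) | coverage | CI wholly below / above truth | Cox HR, coverage |
|---|---|---|---|---|
| 2:1, 8 strata, true 0.635 | 0.610 | 92.7% | 5.7% / 1.7% | 0.635, 95.5% |
| same, true 0.50 | 0.454 | 87.2% | 11.7% / 1.1% | 0.499, 95.4% |
| same, true 0.80 | 0.790 | 93.7% | 3.6% / 2.8% | 0.799, 94.8% |
| same, true 1.0 | 0.997 | 95.4% | 2.1% / 2.5% | 1.000, 95.4% |
| 2:1, no strata, true 0.635 | 0.602 | 91.2% | 7.3% / 1.5% | 0.631, 94.8% |
| 1:1, 8 strata, true 0.635 | 0.630 | 94.0% | 3.3% / 2.7% | 0.632, 94.8% |

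Further runs of the design case gave 0.609 to 0.613 with 92.0–92.2% coverage, against 0.636 to 0.638 and 94.2–95.0% for stratified Cox with Efron ties. A further run at true 0.50 gave 0.456 and 88.7%; at true 0.80, 0.791 and 93.4%.

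**4. Tied event times, true HR 0.635.**

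- Every progression exactly on the nominal visit date: exp(U/V) averages about 0.58, with coverage 91.5–92.1%. Cox with Efron ties on such data gives 0.637 and 95.9%; Cox with Breslow ties gives 0.670.
- Scan dates spread over the ±1 week window: 0.610 to 0.613, with coverage 92.4–92.6%, as for continuous times.

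**5. The test.** The interval excludes 1 exactly when |U|/sqrt(V) > 1.96, which is the log-rank test. One-sided rejection under the null was 2.1%. Power was 89.6%, against 89.5% for Cox.

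**The case against.** The estimator is pre-specified with its formula and citations. Its interval always agrees with the log-rank test, and it is on the same scale as the critical HRs in Section 12.2.1. All of that is true, but agreement with the test is not accuracy of the estimate.

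The size is also modest. ln(0.635/0.610) = 0.040, against a nominal standard error of 1/sqrt(230 × 2/9) = 0.140, so the shift is 0.040/0.140 ≈ 0.29 of a standard error. That stands, and it limits how serious the point is.

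Four stronger readings are tempting, and the protocol does not support them:

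- **A bias down to about 0.58 because of the scan schedule.** This needs every progression to fall exactly on its nominal date. The protocol allows ±1 week, dates PFS by scan and not by visit, counts unscheduled scans, and includes deaths. It also depends on tie handling: on the exact grid, a V without the usual tie correction (the Breslow form) gives 0.650 with 95.4% coverage. Section 12.2.2 both names Breslow and takes V from LIFETEST, so the wording is unclear.
- **Unsafe significance claims.** Decisions on PFS, PFS2 and OS rest on p-values, which do not change.
- **The same size of bias for every endpoint.** No effect is assumed for PFS2 or OS, and at a true HR of 0.80 the bias is slight.
- **An overall point on the forest plot that must look better than its subgroups.** The subgroup Cox models contain only treatment, factor and interaction, so they target a differently adjusted HR and could differ from the overall result anyway. What stands is that two estimators share one plot.

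**Conclusion.** The concern holds at moderate size. At the design HR of 0.635 the planned estimate averages about 0.61, and the nominal 95% interval covers about 92–93%, with roughly 6% of intervals wholly below the truth and 2% above. At a true HR of 0.50 the figures are about 0.454 and 87–89%. The direction rests on the closed form and needs only proportional hazards and 2:1 allocation. The exact sizes rest on the assumed strata, uniform accrual and no dropout; the run without strata shows that stratification does not create the problem. What is at stake is the reported effect size and interval, not any test decision, so this is a should-fix and not a must-fix. The mixed estimators on the forest plot, the Cox HR in Section 12.2.2.1 and the Breslow wording are secondary.

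**What to change.** - In Section 12.2.2, keep the stratified log-rank test for the p-value. Report the HR and 95% CI from a Cox model stratified by the same IVRS/IWRS factors, with Efron ties.
- Apply this to the endpoints that inherit the method: PFS2, OS, TFST and TSST.
- Use that HR as the overall estimate on the forest plot.
- In Section 12.2.2.1, make the Myriad-confirmed analysis consistent with the revised primary analysis, so that any difference between the two reflects the population and not the estimator.
- Remove or correct the Breslow wording attached to LIFETEST.

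The cost is a change of text and one additional model call; the protocol already uses Cox with Efron ties for subgroups. The reported HR will be slightly less favourable, and the Cox interval may disagree marginally with the log-rank p-value at the significance boundary. The text should say that the log-rank test decides. The change should be made before PFS is analysed by arm, so that it cannot look data-driven.

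### A non-significant three-factor interaction test is to be read as proof of a consistent PFS effect, although the test has low power and leaves out six of the nine listed subgroup factors

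*Protocol*

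**What the plan says.** Section 12.2.2 of the protocol lists nine factors for subgroup analysis of PFS. Three are the stratification factors: prior chemotherapy for metastatic disease, hormone receptor status and prior platinum. Six more follow under "Additional subgroups of interest include": progressive disease at randomisation, measurable disease, BRCA mutation type, age, region and race. Each factor gets its own Cox model with treatment, factor and their interaction. The HR and 95% CI for each level go on a forest plot beside the overall result. Subgroups with fewer than 20 events are only described.

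The same section then sets a global test. It compares a Cox model "including treatment, all covariates (stratification factors), and all covariate-by-treatment interaction terms" with one that drops the interactions, at the two-sided 10% level. If the fit is not significantly better, "it will be concluded that overall the treatment effect is consistent across the subgroups". If it is significantly better, backward selection follows, and any interaction found is tested for being qualitative by the Gail and Simon method. The subgroup analyses are declared exploratory and at most supportive of the primary analysis.

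**The concern.** The null hypothesis of the global test is that there is no interaction. Failing to reject it shows only that none was detected, and how much that says depends on the power of the test. The protocol gives no power for it, and the trial is sized for the overall effect alone. The sentence is a fixed rule in the protocol, so an analysis plan that follows it carries the same inference forward.

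The second problem is reach. The model holds three factors, but the conclusion refers to the subgroups without restriction, directly after a list of nine. BRCA mutation type, for example, is outside the test, although section 1.1.1 describes phenotypic differences between BRCA1 and BRCA2 tumours.

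At stake is how the report describes the uniformity of benefit. A material difference in effect between, say, receptor-positive and receptor-negative patients could be written up as a consistent effect.

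**Working it through.** **Inputs from the protocol.** Events: "PFS will be analysed when approximately 230 progression events have occurred, based on the BICR data" (section 12.2.2). Effect and power: the design "would have 90% power to show statistically significant PFS at the one-sided 2.5% level" "if the assumed true treatment effect were HR 0.635" (section 12.3). Allocation is 2:1. The global test has three binary factors, hence three interaction terms (3 df), at the 10% level.

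**The plan's own figure.** By Schoenfeld's formula the required events are (1.960 + 1.282)² / [(ln 0.635)² × (2/3)(1/3)] = 229.3, rounded up to 230. Power at 230 events is 90.1%. The stated figure reproduces, with the 2:1 allocation taken into account.

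**Assumptions of this check.** The protocol does not give the share p of events in one level of each factor, so p runs from 0.2 to 0.5. A 50:50 split favours the test most. In the base case the interaction sits in one factor only.

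**Standard error of a log HR ratio.**

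Var = 1/(230 × 2/9 × p) + 1/(230 × 2/9 × (1 − p)), where 230 × 2/9 = 51.1.

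- p = 0.5: SE = 0.280, so a 95% CI for the ratio spans a factor of exp(1.96 × 0.280) = 1.73 either way.
- p = 0.3: SE = 0.305, a factor of 1.82.
- p = 0.2: SE = 0.350, a factor of 1.98.

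**Power of the global test.** The noncentrality is (ln ratio)² / Var. The 10% critical value of chi-square with 3 df is 6.25. For a ratio of 1.5 and p = 0.5, the noncentrality is 0.1644 / 0.0783 = 2.10.

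| Split | Ratio 1.5, one factor | Ratio 2.0, one factor | Ratio 1.5 in all three factors |
|---|---|---|---|
| 50:50 | 30.5% | 65.2% | 66.3% |
| 40:60 | 29.7% | 63.5% | 64.6% |
| 30:70 | 27.2% | 58.0% | 59.1% |
| 20:80 | 23.0% | 47.8% | 48.7% |

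The last column triples the noncentrality. It assumes independent factors that all have the same split.

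**Simulation check.** The settings were 310 patients, 2:1 allocation, 230 events, 22 months of accrual, a 4-month control median, a likelihood-ratio test of three interactions and 1500 runs per setting. For a ratio of 1.5 in one factor, power was 35% (50:50) and 30% (30:70). For 2.0 it was 68% and 60%. With no interaction the rejection rate was 10-12%. The formula is therefore slightly pessimistic, but not by enough to matter.

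**What the ratios mean.** Around the design HR of 0.635 with a 50:50 split, a ratio of 1.5 gives 0.635/√1.5 = 0.52 and 0.635 × √1.5 = 0.78. A ratio of 2.0 gives 0.45 and 0.90.

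**Frequency of the conclusion.** With one interacting factor, consistency would be concluded in 100 − 31 = 69% to 100 − 23 = 77% of trials at a ratio of 1.5, and in 100 − 65 = 35% to 100 − 48 = 52% at 2.0. For 80% power the ratio would have to be about 2.3 (50:50) or 2.5 (30:70).

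**The case against.** Several points on the other side stand. The analyses are exploratory. The testing procedure for PFS, PFS2 and OS in section 12.2.1 uses no subgroup result, so neither the primary test nor a label claim depends on this sentence. All nine factors have their own interaction models, and the forest plot shows the level-specific HRs and their imprecision whatever the sentence says. The 10% level is a partial allowance for low power, although the figures above already use it. A global test does better when several factors interact. And at ratios of 1.5 and 2.0 around the design HR, both levels still favour olaparib, so a missed interaction would misstate the size of benefit rather than its direction.

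A reader might infer that the plan always declares consistency for the six untested factors. The text does not support that. The conclusion follows only when the global test is non-significant; otherwise selection and the Gail and Simon test follow. Nor is the reach to the six factors certain. The sentence comes directly after a model limited to the stratification factors, and could mean only those. The wording is ambiguous, and the list of nine makes the wider reading natural.

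A reader might also infer that this sentence settles which patients the trial says benefit. It does not, given the exploratory status and the forest plot.

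None of this makes non-rejection into evidence of consistency. Exploratory status explains why there is no multiplicity adjustment; it does not justify the conclusion drawn.

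**Conclusion.** The rule is wrong as written and should be changed. It turns a non-significant result into a positive conclusion, from a test with about 23-31% power for an HR ratio of 1.5 and 48-65% for 2.0 when one binary factor carries the interaction. If all three factors had a ratio of 1.5, power would be about 49-66%. These figures rest on 230 events, 2:1 allocation, a 3-df test at 10% and assumed splits from 20:80 to 50:50. Treating 1.5 or 2.0 as a material difference is a judgement, not a protocol threshold. That non-rejection does not show consistency needs none of these assumptions. The ambiguity over the six factors outside the model is visible in the text. The consequence is limited to how exploratory subgroup results are described.

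**What to change.** Replace the sentence in section 12.2.2 with: *A non-significant global test will be reported as no evidence of heterogeneity detected across the stratification factors; it will not be taken as evidence of consistency and will not be extended to factors outside the model.*

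For each listed subgroup that meets the 20-event minimum, report the treatment-by-factor HR ratio with its 95% CI, from the single-factor Cox models already planned. These intervals will be wide, and showing that is part of the purpose.

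The cost is one sentence and one extra column of output. No new data, no new models and no change to the primary analysis are needed.
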